#### **7.3.2.4. Unconfirmed ORR and Unconfirmed BOR by mRECIST v1.1 – Sensitivity and Supportive Analyses for Confirmed ORR and Confirmed BOR by mRECIST v1.1**

A sensitivity analysis for the ORR assessed under mRECIST v1.1 will be performed using unconfirmed CRs and PRs. The unconfirmed BOR is defined as the best response recorded postbaseline prior to and including the first PD, in the order of CR, PR, SD, PD and NE. For this definition, responses of CR and PR do not need to be confirmed at a subsequent timepoint. In the case of SD, measurements must meet the SD criteria at least once after the date of first dose at a minimum interval of 49 (56 – 7) days. Subjects who fail to meet this criterion will have confirmed BOR of PD if the next available assessment indicates PD or NE if there is no additional assessment available.

Unconfirmed ORR as assessed by mRECIST v1.1 will be summarized by treatment group and dose level for the Phase 1 response evaluable population and by treatment group and tumor type for the Phase 2 response evaluable population.

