### 7.3.2.3. Confirmed ORR and Confirmed BOR by mRECIST v1.1

Under mRECIST v1.1, if radiologic imaging shows CR or PR, a tumor assessment should be repeated at a minimum of 4 weeks to confirm the response in order to claim the CR or PR as the confirmed BOR. If there is no second CR or PR tumor assessment, the CR or PR will be unconfirmed. Table 4 lists the scenarios that can occur after an unconfirmed CR or PR in and provides a rule for determining the confirmed BOR in each scenario. A sensitivity analysis for the ORR assessed under mRECIST v1.1, in which BOR is determined using unconfirmed PR and CR, is detailed in Section 7.3.2.4.

The mRECIST v1.1 instrument was adapted from RECIST v1.1 to include criteria that accounts for new lesions that can occur in immuno-oncology subjects before the occurrence of an SD, PR, or CR. Under mRECIST v1.1, if radiologic imaging shows PD, tumor assessment should be repeated at a minimum of 4 weeks but not more than 6 weeks later to confirm the progression. If there is no second PD tumor assessment in the 4- to 6-week follow-up time, the PD will be defined as unconfirmed. Table 6 lists the scenarios that can occur after an unconfirmed PD in at least 4 weeks and no more than 6 weeks and provides rules for determining whether or not the unconfirmed PD will be counted as an event in the corresponding scenario.

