**Table 6: Rules for Determining PD Event Status After an Unconfirmed PD Under mRECIST v1.1**

Event Occurring After Unconfirmed PD in the Confirmation Window (4-6 weeks)	PD Event Status
Subject had end of study/end of treatment or started new anticancer therapy.	PD will be confirmed as a PD.
Subject had a confirmed PD.	PD will be confirmed as a PD.
Subject had a CR, PR, SD, or NE.	PD will not be considered as a PD and counted as corresponding CR, PR, SD, or NE for the second timepoint only.

Confirmed ORR by mRECIST v1.1 will be summarized by treatment group and tumor type for the Phase 2 response evaluable population.

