#### **7.3.4. Duration of Disease Control and Disease Control Rate**

Duration of disease control (CR, PR, and SD) is defined as the time from the first report of SD or better until disease progression or death from any cause, if occurring sooner than progression, as determined by investigator assessment of radiographic disease per RECIST v1.1 and mRECIST v1.1. Note that the criteria for the assessment of PD in duration of disease control are the same with ORR, which are presented in Section 7.3.2.3.

The duration of disease control will be estimated with 95% CIs overall and by treatment group. Confidence intervals will be calculated based on the exact method for binomial distributions. Swim plots for duration of disease control will be generated separately for RECIST v1.1 and mRECIST v1.1 criteria.

Disease control rate, defined as the proportion of subjects who have disease control (CR, PR, or SD), as per RECIST v1.1 and mRECIST v1.1 will be summarized. For the determination of DCR, response of CR and PR do not need to be confirmed at a subsequent timepoint. In the case of SD, measurements must meet the SD criteria at least after the date of first dose at a minimum of 49 (56 – 7) days. Subjects who fail to meet this criterion will have confirmed BOR of PD if the next available assessment indicated PD or NE if there is no additional assessment available. Disease control rate will be estimated with 95% CIs.

Duration of disease control and DCR as assessed per RECIST v1.1 and mRECIST v1.1 will be summarized by treatment group and dose level for the Phase 1 response evaluable population and by treatment group and tumor type for the Phase 2 response evaluable population.

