2.1.1.2	Summary of Unconfirmed Best Response Under RECIST v1.1 - by Treatment Group and Tumor Type	Phase 2 Response Population		X
2.2.1	Summary of Unconfirmed Best Response, Duration of Response, and Duration of Disease Control Under RECIST v1.1 - by Treatment Group and Dose	Phase 1 Response Evaluable Population		X
2.2.2	Summary of Unconfirmed Best Response, Duration of Response, and Duration of Disease Control Under mRECIST v1.1 - by Treatment Group and Dose	Phase 1 Response Evaluable Population		X
2.2.3.1	Summary of Confirmed Best Response, Duration of Response, and Duration of Disease Control Under mRECIST v1.1 - by Treatment Group and Tumor Type	Phase 2 Response Evaluable Population		X
2.2.3.2	Summary of Unconfirmed Best Response Under mRECIST v1.1 - by Treatment Group and Tumor Type	Phase 2 Response Evaluable Population		X
2.4.1	Summary of Progression-Free Survival Under RECIST v1.1	Phase 1 FAS Population		X
2.4.2	Summary of Progression-Free Survival Under RECIST v1.1 - by Tumor Type	Phase 2 FAS Population		X
2.5.1	Summary of Progression-Free Survival Under mRECIST v1.1	Phase 1 FAS Population		X
2.5.2	Summary of Progression-Free Survival Under mRECIST v1.1 - by Tumor Type	Phase 2 FAS Population		X
2.6.1	Summary of Overall Survival	Phase 1 FAS Population		X
2.6.2	Summary of Overall Survival - by Tumor Type	Phase 2 FAS Population		X

Table No.	Title	Population	Standard	In-Text
Safety				
3.1 Dose Exposure				
3.1.1.1	Summary of Drug Exposure to INCAGN01876 - by Treatment Group and Dose	Phase 1 FAS INCAGN01876 Population		X
3.1.1.2	Summary of Drug Exposure to INCAGN01876 - by Treatment Group and Tumor Type	Phase 2 FAS INCAGN01876 Population		X
3.1.2.1	Summary of Drug Exposure to Nivolumab - by Treatment Group and Dose	Phase 1 FAS Fixed Nivolumab Population		X
3.1.2.2	Summary of Drug Exposure to Nivolumab - by Treatment Group and Dose	Phase 1 FAS Weighted Nivolumab Population		X
3.1.2.3	Summary of Drug Exposure to Nivolumab - by Treatment Group and Tumor Type	Phase 2 FAS Fixed Nivolumab Population		X
3.1.2.4	Summary of Drug Exposure to Nivolumab - by Treatment Group and Tumor Type	Phase 2 FAS Weighted Nivolumab Population		X
3.1.3.1	Summary of Drug Exposure to Ipilimumab - by Treatment Group and Dose	Phase 1 FAS Ipilimumab Population		X
3.1.3.2	Summary of Drug Exposure to Ipilimumab - by Treatment Group and Tumor Type	Phase 2 FAS Ipilimumab Population		X

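### SAP 7.3.2.4 ends mRECIST unconfirmed best response at the first PD without reference to Table 6, and SAP 7.3.4 refers RECIST duration of disease control only to the mRECIST progression rule

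*SAP*

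**What the plan says.** SAP 7.3.2.3 explains that mRECIST v1.1 was adapted from RECIST v1.1 so that it "accounts for new lesions that can occur in immuno-oncology subjects before the occurrence of an SD, PR, or CR". A PD under mRECIST must have its tumor assessment "repeated at a minimum of 4 weeks but not more than 6 weeks later to confirm the progression". When the scan in that window shows NE, SD, PR or CR, Table 6 gives this consequence: "PD will not be considered as a PD and counted as corresponding CR, PR, SD, or NE for the second timepoint only". If the subject instead reaches end of study or end of treatment, or starts new anticancer therapy, Table 6 still counts the PD.

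SAP 7.3.2.4 defines the unconfirmed mRECIST analysis: "The unconfirmed BOR is defined as the best response recorded postbaseline prior to and including the first PD". The same sentence stands in 7.3.2.2 for RECIST v1.1. Neither the word confirmed nor Table 6 is attached to PD.

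SAP 7.3.4 gives a single definition of duration of disease control, "as determined by investigator assessment of radiographic disease per RECIST v1.1 and mRECIST v1.1". It then notes that "the criteria for the assessment of PD in duration of disease control are the same with ORR" and gives 7.3.2.3 as the only place where those criteria are found.

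In Appendix A, Table 2.2.2 is titled "Summary of Unconfirmed Best Response, Duration of Response, and Duration of Disease Control Under mRECIST v1.1" and is planned for the Phase 1 response evaluable population.

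**The concern.** The two criteria differ in what counts as progression. RECIST v1.1 stops at the first PD. mRECIST v1.1 sets aside a PD that the repeat scan does not bear out. An endpoint labelled with one criterion should use that criterion's rule, and two definitions in the SAP do not secure this.

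In 7.3.2.4, a literal programmer stops an mRECIST best response at a PD that Table 6 says is not a PD, and a later CR or PR is not counted. In 7.3.4, a literal programmer carries a RECIST duration past the RECIST progression date.

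Three outputs are at stake:
- the Phase 1 mRECIST response summary (Table 2.2.2), which is the only planned Phase 1 mRECIST response table, because 7.3.2.3 plans the confirmed mRECIST ORR summary for Phase 2 only;
- the Phase 2 unconfirmed mRECIST sensitivity analysis;
- RECIST duration of disease control, which could disagree with RECIST PFS in the same subject.

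**Working it through.** The plan states no figure on this point, so the check compares definitions and then applies both rules to example scan sequences.

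**Step 1. The PD that ends each endpoint, as written in the SAP.**

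| Endpoint | RECIST v1.1 | mRECIST v1.1 |
|---|---|---|
| Unconfirmed BOR | first PD (7.3.2.2) | first PD, same sentence (7.3.2.4) |
| DOR | first PD (7.3.3.1) | first confirmed PD, referring to 7.3.2.3 (7.3.3.2) |
| Duration of disease control | referred to 7.3.2.3 (7.3.4) | referred to 7.3.2.3 (7.3.4) |
| PFS | first PD (7.3.7.1) | first confirmed PD, referring to Table 6 (7.3.7.2) |

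DOR and PFS are split by criterion. Unconfirmed BOR has the RECIST rule in both columns, and duration of disease control has the mRECIST rule in both. SAP 9.1.2.1 also counts a CR or PR seen 4 to 6 weeks after an unconfirmed PD, which agrees with Table 6 and not with a literal 7.3.2.4.

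**Step 2. Best response.** Assume that the scan after the PD falls within the 4 to 6 week window.
- Scans PD, PR: the literal 7.3.2.4 gives PD; Table 6 gives PR.
- Scans SD, PD, PR: the literal 7.3.2.4 gives SD; Table 6 gives PR.

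There are 135 sequences of 2 to 4 scans, each CR, PR, SD or PD, in which the first PD is followed by a non-PD scan. The two rules give a different best response in 87 of them. In 70 of those 87, a responder under Table 6 becomes a non-responder. These are counts of possible patterns, not probabilities.

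**Step 3. Duration of disease control.** Illustrative subject: SD on day 57, PD on day 113, SD on days 148 and 169, PD on day 225 confirmed on day 260.
- Repeat scan after the first PD: 148 − 113 = 35 days, which is 5 weeks and inside the window, so Table 6 discards that PD.
- First-PD rule: 113 − 57 = 56 days.
- Table 6 rule: 225 − 57 = 168 days.
- Difference: 168 − 56 = 112 days. RECIST PFS for this subject has its event on day 113, while RECIST disease control as written in 7.3.4 runs to day 225.

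**Step 4. Weight of one affected subject.** The documents do not say how many subjects have a reversed PD, so the counts below are assumptions.
- Phase 2 sensitivity analysis, full cohorts of 46 to 51 (SAP Table 2): one lost responder is 1/51 = 2.0 to 1/46 = 2.2 percentage points. Three are 3/51 = 5.9 to 3/46 = 6.5 points.
- Phase 1, 3 to 9 evaluable subjects per dose cohort (SAP 3.4.1): one lost responder is 1/9 = 11.1 to 1/3 = 33.3 points. Those are the dose-escalation counts; the response evaluable denominators may differ.

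**The case against.** There is a good case that the authors intended the right rules. SAP 7.3.2.3 describes the sensitivity analysis as one "in which BOR is determined using unconfirmed PR and CR, is detailed in Section 7.3.2.4", so only response confirmation is relaxed and nothing says that PD confirmation is dropped. If Table 6 is applied first, a discarded PD is no longer a PD, and the first PD in an mRECIST section means the first one that survives. In 7.3.4, the note resembles the one in 7.3.3.2 and may have been carried over from it. The section it points to limits its own confirmation rule to mRECIST, and RECIST ORR in 7.3.2.1 uses the first PD.

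This stands as evidence of intention. It does not settle the text. Where the SAP wants confirmed PD, in 7.3.3.2 and 7.3.7.2, it says so; 7.3.2.4 does not. The note in 7.3.4 is not limited to mRECIST and cites no RECIST section. Two programmers could reasonably code different rules.

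Several stronger readings are tempting and not supported:
- *The mRECIST unconfirmed result must duplicate the RECIST result.* This follows only on the literal reading. With Table 6 applied first, the two can differ.
- *Every unconfirmed PD moves the end of RECIST disease control.* It does not. Table 6 counts a PD followed by end of treatment, end of study or new anticancer therapy, and those dates stay where they are.
- *The Phase 1 mRECIST response endpoint is lost.* The summary table is exposed, but Listing 2.5.2.1 gives mRECIST best response with confirmed CRs and PRs and is not restricted by phase. Phase 1 mRECIST DOR and PFS use confirmed PD.
- *mRECIST ORR in Phase 2 is biased by a known amount.* The confirmed analysis follows 7.3.2.3 and Table 6 and is unaffected. Any figure for the unconfirmed analysis rests on an assumed share of subjects.

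**Conclusion.** The point holds in a limited form. As written, 7.3.2.4 gives mRECIST unconfirmed best response the RECIST cut-off, and 7.3.4 points RECIST duration of disease control at the mRECIST progression rule. Followed literally, both conflict with the SAP's own definitions elsewhere, so they need correcting and not merely more detail. For 7.3.2.4, the intended rule is probably Table 6, and the defect is that the section does not say so.

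The reach is narrow. Only subjects whose PD is followed in the 4 to 6 week window by CR, PR, SD or NE can differ. Their share is unknown from the documents, so no overall shift in ORR or in duration can be stated; the per-subject figures show scale only. The exposed outputs are secondary or supportive. The primary confirmed RECIST ORR, the Simon error rates and the Phase 2 confirmed mRECIST ORR are not affected.

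**What to change.** Change two sentences in the SAP:
- In 7.3.2.4, define unconfirmed BOR as the best response *up to and including the first PD that counts as an event under Table 6*.
- In 7.3.4, replace the note with: *PD is the first assessment of PD for RECIST v1.1 (as in 7.3.3.1 and 7.3.7.1) and the first PD that counts as an event under Table 6 for mRECIST v1.1 (as in 7.3.3.2 and 7.3.7.2)*.

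This extends to both endpoints the split already used for DOR and PFS. It needs no new data; the programming specification for the affected tables should be checked against the revised text.

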#### **7.3.3. Duration of Response**

Duration of response will be assessed with RECIST v1.1 and mRECIST v1.1 criteria.

Censoring of DOR will follow the same algorithm as the censoring of PFS (as described in Section 7.3.7). Kaplan-Meier curves for DOR will be presented by cohort-specific tumor types. The KM estimate of median DOR will be presented with its 95% CI. The 95% CI will be calculated using Brookmeyer and Crowley's method ([Brookmeyer and Crowley 1982](#)). A swim plot for DOR will be generated under both RECIST v1.1 and mRECIST v1.1 criteria.

Duration of response as assessed by RECIST v1.1 and mRECIST v1.1 will be summarized by treatment group and dose level for the Phase 1 response evaluable population and by treatment group and tumor type for the Phase 2 response evaluable population.

##### **7.3.3.1. Duration of Response by RECIST v1.1**

Under RECIST v1.1, for unconfirmed objective responders, DOR is defined as the time from the first overall response contributing to an unconfirmed objective response (CR or PR) to the earlier of the subject's death from any cause or first assessment of PD.

##### **7.3.3.2. Duration of Response by mRECIST v1.1**

Under mRECIST v1.1, for unconfirmed objective responders, DOR is the time from the first unconfirmed overall response contributing to an unconfirmed objective response (CR or PR) to the earlier of the subject's death from any cause or first confirmed assessment of PD. Note that the criteria for the assessment of PD in DOR are the same with ORR, which are presented in Section 7.3.2.3.

#### **7.3.4. Duration of Disease Control and Disease Control Rate**

Duration of disease control (CR, PR, and SD) is defined as the time from the first report of SD or better until disease progression or death from any cause, if occurring sooner than progression, as determined by investigator assessment of radiographic disease per RECIST v1.1 and mRECIST v1.1. Note that the criteria for the assessment of PD in duration of disease control are the same with ORR, which are presented in Section 7.3.2.3.

The duration of disease control will be estimated with 95% CIs overall and by treatment group. Confidence intervals will be calculated based on the exact method for binomial distributions. Swim plots for duration of disease control will be generated separately for RECIST v1.1 and mRECIST v1.1 criteria.

Disease control rate, defined as the proportion of subjects who have disease control (CR, PR, or SD), as per RECIST v1.1 and mRECIST v1.1 will be summarized. For the determination of DCR, response of CR and PR do not need to be confirmed at a subsequent timepoint. In the case of SD, measurements must meet the SD criteria at least after the date of first dose at a minimum of 49 (56 – 7) days. Subjects who fail to meet this criterion will have confirmed BOR of PD if the next available assessment indicated PD or NE if there is no additional assessment available. Disease control rate will be estimated with 95% CIs.

Duration of disease control and DCR as assessed per RECIST v1.1 and mRECIST v1.1 will be summarized by treatment group and dose level for the Phase 1 response evaluable population and by treatment group and tumor type for the Phase 2 response evaluable population.

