6.4.2. Disease Status Follow-Up

Subjects who discontinue study treatment for a reason **other than** disease progression (eg, toxicity) will move into the disease status follow-up period and should be assessed every 8 weeks (\pm 7 days), for 12 months. After 12 months, radiologic assessments will be performed every 12 weeks until disease progression is determined. Every effort should be made to collect information regarding disease status until:

- The start of new antineoplastic therapy.
- Disease progression.
- Death.
- The end of the study.
- Withdrawal of consent.

Note: As of Protocol Amendment 5, disease status follow-up will no longer be required beyond the last safety follow-up visit for subjects who discontinue study treatment for a reason other than disease progression. The last disease status follow-up data will be recorded in the eCRF at the time of the last safety follow-up visit. The last study visit will be the last safety follow-up visit.

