9.4.1.2. Secondary Efficacy Analyses

Disease control rate, defined as the proportion of subjects who have disease control (CR + PR + SD), as per RECIST v1.1 and mRECIST v1.1 will be summarized.

Progression-free survival, DOR, and duration of disease control will be estimated using the Kaplan-Meier method as per RECIST v1.1 and mRECIST v1.1. Overall survival will be estimated using the Kaplan-Meier method.

In Phase 2, the proportion of subjects who meet the objective response criteria (CR + PR) per RECIST v1.1 and mRECIST v1.1 will be summarized by tumor type.

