**7.3.2.1.1. Subgroup Analyses for Confirmed Best Overall Response Under RECIST v1.1 in Phase 2**

Subgroups will be formed based on the following subject characteristics and baseline variables for those subjects enrolled in Phase 2 of the study whose data are available.

- PD-L1 expression within tumor type: high, negative/low, unknown
- Number of prior therapies for advanced and metastatic disease within tumor type
- Subjects with > 1 postbaseline scan within tumor type
- Tumor-type disease characteristics including the following:
  - Endometrium – MSI status (high, low, stable, unknown)
  - SCCHN – human papilloma virus status (positive vs negative)

**7.3.2.2. Unconfirmed ORR and Unconfirmed BOR by RECIST v1.1 – Sensitivity and Supportive Analyses for Confirmed ORR and Confirmed BOR by RECIST v1.1**

A sensitivity analysis for the ORR assessed under RECIST v1.1 will be performed using unconfirmed CRs and PRs. The unconfirmed BOR is defined as the best response recorded postbaseline prior to and including the first PD, in the order of CR, PR, SD, PD, and NE. For this definition, responses of CR and PR do not need to be confirmed at a subsequent timepoint. In the case of SD, measurements must meet the SD criteria at least once after the date of first dose at a minimum interval of 49 (56 – 7) days. Subjects who fail to meet this criterion will have BOR of PD if the next available assessment indicates PD or NE if there is no additional assessment available.

Unconfirmed ORR will be summarized by treatment group and tumor type as a sensitivity analysis for the primary endpoint ORR for the Phase 2 Response Evaluable Population and as a sensitivity analysis for the secondary endpoint ORR for the Phase 1 Response Evaluable Population.

### 7.3.2.2.1. Subgroup Analyses for Unconfirmed Best Overall Response by RECIST v1.1 in Phase 1

For the sensitivity analysis for unconfirmed BOR, subgroups will be formed based on the following subject characteristics and baseline variables for those subjects enrolled in Phase 1 of the study whose data are available.

- Prior treatment with an anti-PD-1/PD-L1 therapy within tumor type: Yes/No

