### 10.1. Changes to Protocol-Defined Analyses

Not applicable.

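### SAP 7.3.4 puts an exact binomial interval on duration of disease control, a censored time for which the protocol specifies Kaplan-Meier; Phase 2 duration of response also does not match the confirmed-response tables that carry it

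*SAP*

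**What the plan says.** **Duration of disease control.** SAP 7.3.4 defines it as the time from the first report of stable disease or better to progression or death. It promises 95% intervals for this duration, overall and by treatment group, and the next sentence reads "Confidence intervals will be calculated based on the exact method for binomial distributions". The section names no estimator, no interval method for a median and no censoring rule; it adds only swim plots and a pointer to the criteria for progression. For the rate it says "Disease control rate will be estimated with 95% CIs" and stops.

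Protocol 9.4.1.2 says "Progression-free survival, DOR, and duration of disease control will be estimated using the Kaplan-Meier method". SAP 10.1, headed "Changes to Protocol-Defined Analyses", is marked not applicable.

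**Duration of response (DOR).** SAP 7.3.3 uses Kaplan-Meier with a Brookmeyer-Crowley interval for the median, and "Censoring of DOR will follow the same algorithm as the censoring of PFS". The definition in SAP 7.3.3.1 is that "for unconfirmed objective responders, DOR is defined as the time from the first overall response contributing to an unconfirmed objective response"; 7.3.3.2 does the same for mRECIST. No confirmed-responder version is given. SAP 7.3.2.1 makes confirmed ORR the Phase 2 primary endpoint. Appendix A places Phase 2 DOR only in Tables 2.1.1.1 and 2.2.3.1, both of which summarise confirmed best response.

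**The concern.** A binomial interval is for a proportion. Duration of disease control is a time, and some subjects will be censored. Followed literally, the SAP gives this endpoint a method that conflicts with the protocol and leaves the disease control rate, to which the method would apply, with none. The departure is undeclared, so nothing tells the programmer which document governs.

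Censoring will occur. Subjects who stop treatment without progression, start new therapy or miss assessments would be censored under rules like SAP Table 7. Amendment 5 adds a further source where treatment ends without progression, because Protocol 6.4.2 now states: "disease status follow-up will no longer be required beyond the last safety follow-up visit for subjects who discontinue study treatment".

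The methods for DOR are sound, but the subjects are not those of the table. A reader of Table 2.1.1.1 would take DOR to describe the confirmed responses counted there. As defined, it also covers subjects whose response was never confirmed.

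**Working it through.** **1. Duration of disease control: the texts side by side**

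| Endpoint | Protocol 9.4.1.2 | SAP estimator | SAP interval | SAP censoring |
|---|---|---|---|---|
| PFS | Kaplan-Meier | Kaplan-Meier (7.3.7) | Brookmeyer-Crowley | Table 7 |
| DOR | Kaplan-Meier | Kaplan-Meier (7.3.3) | Brookmeyer-Crowley | as PFS |
| Duration of disease control | Kaplan-Meier | none stated (7.3.4) | exact binomial | none stated |
| Disease control rate | summarised | proportion (7.3.4) | 95%, no method | not applicable |

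The third row is out of line with both the protocol and the rest of the SAP. The version gap does not evidently explain it. The SAP was written on Amendment 2 but remains in force for later amendments (SAP 2.1), and the summaries for Amendments 3 to 5 list no change to Protocol 9.4.1.2.

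**2. What a binomial interval for a duration would do**

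The plan has no figure to reproduce. The most charitable reading is the order-statistic interval for a median, whose ranks come from the binomial distribution. Assumptions, none of them from the documents: exponential durations with median *m*, independent exponential censoring with expected share *c*, censored times counted as events, and *n* = 15, 25 or 40 subjects with disease control.

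- The observed time is then exponential with median *m*(1 − *c*). The naive median is therefore about 0.80 of the truth at *c* = 0.20 and 0.60 at *c* = 0.40.
- The chance that an observed time is at or below *m* is *q* = 1 − 0.5^(1/(1 − *c*)). At *c* = 0.20, *q* = 1 − 0.5^1.25 = 0.580.
- With interval ranks *l* to *u*, coverage is P(*l* ≤ B ≤ *u* − 1), where B is binomial(*n*, *q*). The ranks are 4–12 (*n* = 15), 8–18 (*n* = 25) and 14–27 (*n* = 40).

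Exact coverage of the nominal 95% interval:

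| Censored | *q* | *n* = 15 | *n* = 25 | *n* = 40 |
|---|---|---|---|---|
| 0% | 0.500 | 96.5% | 95.7% | 96.2% |
| 10% | 0.537 | 95.7% | 94.2% | 94.0% |
| 20% | 0.580 | 93.0% | 88.8% | 85.5% |
| 30% | 0.629 | 86.7% | 76.7% | 66.7% |
| 40% | 0.685 | 74.5% | 55.3% | 37.3% |

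In a simulation of the same settings (10,000 replications per cell), Kaplan-Meier with a log-log Brookmeyer-Crowley interval covered 93.8% to 95.6% in every cell, and at *n* = 25 the Kaplan-Meier median was 1.00 to 1.01 times the truth. The binomial interval becomes worse as *n* grows because it narrows around a biased value.

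**3. DOR against its tables**

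- SAP 7.3.2.2 defines unconfirmed best response so that "responses of CR and PR do not need to be confirmed at a subsequent timepoint". They may still be confirmed, so the DOR set is all confirmed responders plus those never confirmed.
- In Phase 1 the definition and the tables agree: Tables 2.2.1 and 2.2.2 report unconfirmed response with DOR.
- In Phase 2 they do not. DOR is only in the confirmed-response tables; the unconfirmed tables, 2.1.1.2 and 2.2.3.2, carry none.
- Example: partial response, then progression at the next scan. SAP Table 4 makes this stable disease or progression, not a confirmed response. Under 7.3.3.1 the same subject contributes a DOR running from the response to that progression. The table could then show more subjects with a DOR than responders.
- Subjects who progress or die before confirmation add short durations. A partial response followed by stable disease, or with no later valid scan, does not add a short event time. The net effect cannot be estimated from the documents.

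**The case against.** The binomial sentence is almost certainly a slip: it fits the disease control rate, which lacks a method. The SAP says it gives detail to the protocol's analyses, so the protocol's Kaplan-Meier estimator arguably still stands, and a programmer would query a binomial interval for a time. That explanation is likely, but the text still needs correcting, because it also leaves the censoring rule and the rate's interval method unstated.

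The coverage figures need two steps the SAP does not prescribe: an order-statistic reading, and counting censored times as events. At 10% censoring the loss is trivial (94.2% at *n* = 25). This stands. The figures show what goes wrong if censoring is ignored; they do not forecast this trial's result.

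Amendment 5 may add little censoring. Its rationale says enrolment was complete, ongoing subjects had been on treatment for more than 15 months or were in follow-up, and data sufficed for the primary and secondary endpoints. This stands as a limit on that one source; ordinary censoring under Table 7-type rules remains.

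On DOR, the SAP states its basis openly, the protocol's definition does not mention confirmation, the same tables also hold duration of disease control, and the table shells, which may carry a footnote, are in a separate document. So this half is partly a labelling matter. The mismatch between definition and table title remains in the text available.

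**Conclusion.** The point holds. SAP 7.3.4 is wrong as written: it assigns a method for proportions to a censored time, conflicts with Protocol 9.4.1.2 without declaring a change, and leaves the disease control rate without an interval method. If the sentence were applied as an order-statistic interval that ignores censoring, coverage at 25 subjects would be 88.8% at 20% censoring and 55.3% at 40%, with the median understated by about 20% and 40%. This assumes exponential durations, independent censoring, and a sample size and censoring shares that the documents do not give.

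The Phase 2 DOR mismatch also holds, as a smaller point of unknown size. Both endpoints are secondary. Confirmed ORR, the Simon rules and the Bayesian futility rule are unaffected. The correction should be made before the final analysis.

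**What to change.** - **SAP 7.3.4:** estimate duration of disease control by Kaplan-Meier, with a Brookmeyer-Crowley 95% interval for the median and Table 7 censoring. Assign the exact binomial interval to the disease control rate.
- **SAP 7.3.3:** define the main Phase 2 DOR for confirmed responders, from the first assessment of the response later confirmed. Keep the present definition for Phase 1 and as a Phase 2 sensitivity analysis.
- **At minimum:** footnote Tables 2.1.1.1 and 2.2.3.1 to say which responders the DOR covers, and show their number.

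The cost is SAP wording and one changed procedure call, using methods the SAP already applies elsewhere. Confirmed-responder DOR has fewer subjects. It also excludes those who progress before the confirmatory scan, and since confirmation comes at least 4 weeks later and before progression, every duration in it is at least that long. This is why the unconfirmed version is worth keeping alongside.
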